5.1 Overview

This is a multicenter, prospective, single-arm confirmatory diagnostic accuracy study. EGD is the reference standard against which ds-MCE is compared, and it is performed within 48 hours after ds-MCE examination.

5.2 Eligibility criteria

5.2.1 Inclusion Criteria

Subjects meeting all of the following criteria are eligible for enrollment as study participants:

- (1) Gender is not limited.
- (2) Patients aged 18 years or older.
- (3) Both inpatients and outpatients.
- (4) Clinically evident or biopsy-proven liver cirrhosis.
- (5) Able to provide informed consent.

5.2.2 Exclusion Criteria

Subjects meeting any of the following criteria are not eligible for enrollment as study

participants:

- (1) Patients aged less than 18 years.
- (2) Patients with dysphagia.
- (3) Patients with Zenker's diverticulum.
- (4) Suspected or known intestinal stenosis or other known risk factors for capsule retention.
- (5) Pregnancy or suspected pregnancy.
- (6) Patients with active gastrointestinal bleeding.
- (7) Patients with cardiac pacemaker or other implanted electromedical devices which could interfere with magnetic resonance.
- (8) Patients with life-threatening conditions.
- (9) Patients plan to undergo magnetic resonance imaging examination before excretion of the MCE.
- (10) Patients who are participating in or have participated in other clinical trials.
- (11) Patients who refuse to give informed consent.
- (12) Patients with any condition that precludes compliance with the study.

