6.2 The ds-MCE and EGD examination procedures

6.2.1 The ds-MCE system and examination procedure

6.2.1.1 The ds-MCE system

The ds-MCE system (Ankon Technologies Co., Ltd, Wuhan, China) mainly consists of two parts: the NaviCam magnetically maneuvered capsule endoscopy (MCE) system and a detachable latex hollow string attachment.

The MCE system consists of a guidance magnet robot, an endoscopic capsule, a capsule locator, a computer workstation with ESNavi software, and a data recorder (Fig. 2). The capsule has a size of 27×11.8 mm, weighs 4.8 g and has a permanent magnet inside its dome. Images are captured and recorded at 0.5-6 frames per second (fps) with a resolution of 480×480 pixels. The view angle of the capsule is 150°, and the view depth is 0 to 60 mm. The battery life of the capsule is more than 10 hours. The guidance magnet robot is a C-arm type robot, with two rotational and three translational degrees of freedom. The magnetic field generated by the magnetic robot can reach a maximum of 200mT and is adjustable. The computer workstation with ESNavi software is

designed for real-time viewing and controlling. The capsule locator is a device for activating the capsule and detecting whether it is inside the human body. The data recorder is used for receiving image data via wireless transmission from the capsule endoscope. There are two joysticks on the workstation desktop (Fig. 3). The left joystick controls capsule orientation in 2 rotational axes (horizontal and vertical directions), and the right one controls capsule location in 3 translational axes (forward/backward, up/down, left/right). The detachable latex hollow string is 120cm in length, with a thin latex sleeve at one end that can be attached to the capsule endoscopy and a thick latex sleeve at the other end that can be attached to the syringe (Fig. 4). The capsule, which is partially enclosed within the sleeve, can be actively moved in the esophagus through the control of string. After completion of the esophageal examination, the string can be separated from the capsule by injecting around 5mL of air using the syringe and removed from the mouth; the capsule then enters the stomach.

Figure 2. The NaviCam magnetically maneuvered capsule endoscopy (MCE) system. It consists of (A) a guidance magnet robot and computer workstation; (B) a magnetic capsule endoscope; (C) a capsule locator; (D) ESNavi software; (E) a data recorder.

[figure not shown]

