During esophageal examination, the capsule will be actively controlled by the latex hollow string. Before ingestion of the capsule, the CE is partially enclosed in the sleeve that could be detached from the string system through injecting air into the hollow string with the syringe (Fig. 4). Patient then swallows the capsule with water in a left lateral position, without sedation, and the capture rate of the capsule is set as 6 frames per second. Firstly, the CE will be allowed to travel down approximating the cardia, from where the string is slowly pulled up to inspect the esophagus under the guidance of real-time viewing. The process will be repeated for at least three passages up and down, during which participants will be instructed to drink water to distend the distal esophagus and wash bubbles for better observation. Target areas of interest could be observed repeatedly as the capsule travels down with swallowed water and be pulled up by attached string. After completing the esophageal examination, the string will be separated from the capsule through injecting 5 ml of air with the syringe, took out of the mouth and discarded, and the capsule will enter the stomach with additional water ingestion.

(3) Stomach examination of ds-MCE

During the gastric examination, the capsule will be actively controlled by external magnetic field. When the capsule entering the stomach, the capsule will be lifted away from the posterior wall, rotated, and advanced to the fundus and cardiac regions, and then to the gastric body, angulus, antrum, and pylorus. Of note, target areas of interest

could be observed repeatedly. If distension is insufficient, water ingestion will be repeated. Stomach examination procedures will be performed twice in each participant according to standardized protocol^{46,47}, and the mucosa of the gastric cardia, fundus, body, angulus and antrum will be fully recorded. Once the operator is satisfied that an adequate examination of stomach has been completed the capsule will be allowed to pass into the small bowel.

(4) Small bowel examination of ds-MCE

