10.3 Benefits and risks assessment

Knowledge gained from this study may benefit society by improving EGV and PHE screening and surveillance for cirrhotic patients in the future. Study participants may benefit directly from the study because they will be provided with a free ds-MCE procedure and a free standard EGD examination that can fully evaluate the upper gastrointestinal mucosa and small intestine mucosa. The main risk of ds-MCE is retention of the capsule behind a stricture, occurring in around 1% of patients with suspected small bowel disease^{45,47}. When patients undergo the EGD examination, there is potential for procedure-related complications, such as bleeding. These risks will be small since careful procedure will be provided in the study.

Given the minimal risks associated with this study and the potential benefits to society and individuals, the benefits outweigh the risks. As for any clinical study, there is a possibility of unknown and unforeseen risk; that possibility is small for this study. If unforeseen risks are recognized during the study, then the sponsor, ethics committees, and participants will be provided with relevant information.

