To overcome these limitations, a new technique, so-called detachable string magnetically maneuvered capsule endoscopy (ds-MCE) (Ankon Technologies, Wuhan, China) was developed. The ds-MCE system consists of two parts: the magnetically maneuvered capsule endoscopy (MCE) system and a transparent latex sleeve with a hollow string. The capsule, which is partially enclosed within the sleeve, can be actively

moved in the esophagus by the control of string. After completion of the esophageal examination, the string could be separated from the CE by injecting 5mL of air and removed from the mouth; the CE continued into the stomach. During the gastric examination, CE can be actively controlled by external magnetic field. Previous studies have demonstrated that the diagnostic accuracy of MCE for detecting gastric focal lesions is comparable with that of conventional EGD. Two pilot studies of ds-MCE confirmed it was a feasible, safe and well-tolerated method for detecting EGV in patients with cirrhosis. Besides, the 8-10h battery life of the ds-MCE enables further evaluation of the portal hypertensive enteropathy (PHE) in small-bowel, providing a more comprehensive evaluation of gastrointestinal changes in cirrhotic patients.

The study of magnetically maneuvered Capsule ENdoscopy for deTection of Esophagogastric vaRices in patients with cirrhosiS (CENTERS) is a multicenter, prospective diagnostic accuracy study, assessing the diagnostic performance of ds-MCE in detecting and grading EGV in patients with cirrhosis, using EGD as the reference.

4. Study Objective

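### The string and sleeve used in the esophagus are latex, but the exclusion criteria omit latex allergy, so a patient known to be allergic is eligible as written

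*SAP*

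**What the plan says.** **Device.** Protocol 6.2.1.1 states: "The detachable latex hollow string is 120cm in length, with a thin latex sleeve at one end". Protocol 1 describes the device in the same way. The SAP background is briefer and speaks of "a transparent latex sleeve with a hollow string". It names latex for the sleeve only and gives no length.

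**Use.** Protocol 6.2.1.2 (2) states: "During esophageal examination, the capsule will be actively controlled by the latex hollow string". The capsule, partly enclosed in the sleeve, is swallowed without sedation. It travels down to near the cardia, "from where the string is slowly pulled up to inspect the esophagus under the guidance of real-time viewing". Then: "The process will be repeated for at least three passages up and down". The opening of 6.2.1.2 applies ds-MCE to every enrolled patient.

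**Eligibility.** Protocol 5.2 and SAP 5.2.2 carry the same 12 exclusions, ending with "Patients with any condition that precludes compliance with the study". The synopsis gives a shorter list with an equivalent last item. Protocol 5.3 has the investigator or a nominee check each candidate against the inclusion and exclusion criteria before consent and enrollment.

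**Risk and baseline.** Protocol 4.2 names capsule retention, nausea that may lead to variceal bleeding, and EGD complications. Protocol 10.3 says "The main risk of ds-MCE is retention of the capsule behind a stricture" and adds EGD complications. Protocol 6.1 lists medical history and comorbidities by example, and allergy is not among the examples.

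**The concern.** The eligibility list is where this plan controls hazards that come from the device. It does so for the magnet, for retention and for swallowing. The material that touches the patient is stated in the Protocol itself, so a reaction in a patient known to be allergic to it can be foreseen from the plan's own text. Yet none of the places that would catch it (exclusions, baseline record, risk account) mentions it.

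What is at stake is patient safety, in a study whose risk-benefit statement (Protocol 4.3 and 10.3) rests on risks being minimal and whose consent section (10.2) requires foreseeable risks to be explained. Adverse-event recording under Protocol 7.1 would pick up a reaction, but only after exposure.

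**Working it through.** No arithmetic applies, and the plan states no figure to reproduce. The check sets the sections side by side.

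1. **Is there latex contact in the esophagus?** Yes. Protocol 1 and 6.2.1.1 give latex for both string and sleeve, and 6.2.1.2 (2) puts them in the esophagus for at least three passages. The SAP confirms the sleeve only.

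2. **Who is exposed?** All enrolled patients (Protocol 6.2.1.2); 591 are planned.

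3. **Does any exclusion cover it?** The 12 items of Protocol 5.2, grouped by what they address:

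| Group | Items | Covers latex allergy? |
|---|---|---|
| Swallowing or passage of the capsule | dysphagia; Zenker's diverticulum; stenosis or other retention risk | No |
| Magnet or MRI | pacemaker or other implanted device; MRI planned before excretion | No |
| Clinical state | pregnancy; active gastrointestinal bleeding; life-threatening conditions | No |
| Administrative | age under 18; other trials; refusal of consent | No |
| Catch-all | condition precluding compliance | Not by its wording |

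   The count is 3 + 2 + 3 + 3 + 1 = 12 items, of which 0 name latex or allergy. SAP 5.2.2 also has 0 of 12, and the synopsis list has none.

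4. **Could two items be stretched to fit?** A patient with a known allergy can keep to every study requirement, so the allergy does not in itself preclude compliance. An allergy that is not active is not naturally described as a life-threatening condition.

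5. **Does another section supply the check?** Protocol 5.3 ties the eligibility check to the listed criteria. Protocol 6.1 permits allergy to be recorded, because its lists are open, but does not require it. Protocol 4.2 and 10.3 do not mention latex.

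6. **Result.** A patient who meets the inclusion criteria and has a known latex allergy, with none of the 12 listed exclusions, is eligible on the text.

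**The case against.** The strongest case on the other side is that this is only an omission from a list, and that practice would fill it. An investigator assesses every candidate and must explain foreseeable risks. Someone who cannot safely undergo the mandatory string procedure could be kept out under the catch-all. Consent pages were removed from the supplied documents and the device labelling is not supplied, so a latex warning may exist in either. The baseline lists are open, and Protocol 10.3 speaks of the main risk, not of all risks.

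Much of this stands. It means that exposure depends on discretion, not that the criteria cover the case. The list already spells out other device hazards instead of leaving them to judgement at 14 centers, and a warning elsewhere would be a reason to carry it into Protocol 5.2.

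The timing objection also stands. The SAP was first drafted on 27 April 2023 and finalised on 19 May 2023, while the synopsis places first patient in to last patient out between January 2021 and January 2023. A new exclusion in the SAP alone would protect nobody and could make the SAP differ from the criteria applied. Protocol 5.2 governs.

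Several stronger readings are tempting, and the documents do not support them:

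- **Allergic patients were enrolled.** The text shows eligibility only.
- **Contact is prolonged.** A minimum of three passages is given, but no planned contact time.
- **A reaction would necessarily stop the esophageal examination.** Nothing in the documents establishes this.
- **A number of patients at risk can be stated.** Any such number would need an outside allergy rate applied to the 591.
- **The SAP also describes a latex string drawn repeatedly through the esophagus.** It mentions only the latex sleeve.

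**Conclusion.** The point holds as a gap in safety eligibility: the Protocol exposes every enrolled patient to latex in the esophagus, and its exclusion list leaves a patient known to be allergic eligible unless the investigator uses discretion. Its extent is one missing criterion, with matching silence in the baseline and risk sections. How many patients it touches cannot be said from the documents.

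A reader might infer damage to the accuracy results. The documents do not support that: the sample size, the hypotheses and the analysis of sensitivity and specificity do not depend on this criterion.

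The conclusion rests on reading the catch-all by its wording, and on the exclusion lists being complete as shown. It would weaken in practice, though not on the text, if the device labelling or the consent form already bars these patients. This is a cheap improvement for patient safety, not a threat to the study's conclusions.

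**What to change.** Reconcile the eligibility criteria with the device description and the device labelling:

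- **Protocol 5.2:** add known latex allergy, and carry it into the synopsis list. If the labelling already bars these patients, use its terms.
- **Protocol 6.1:** make latex allergy a required baseline item.
- **Protocol 4.2 and 10.3:** name reaction to latex among the risks, with the consent form to match if it does not already do so.
- **SAP 5.2.2:** change it only to mirror the Protocol; it should not carry a criterion that the Protocol lacks.

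**Cost.** A few patients could not be enrolled. The text changes are short, but they form a minor amendment that needs ethics review across the 14 centers, plus one case report form item. If enrollment has already closed, as the synopsis dates suggest, the change serves the written record, reporting and any reuse of the protocol.

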5.3 Sample size

As a single-arm confirmatory diagnostic accuracy study, we primarily aimed to test whether both the sensitivity and the specificity of ds-MCE for detecting EGV would be $>85\%$. With estimated sensitivity of 90%, specificity of 94%, a two-sided alpha of 5%, power of 80%, EGV prevalence of 62%, and a dropout rate of 3%, 591 patients would be needed¹.

When considering the accuracy of ds-MCE for detecting high-risk EV (key secondary outcome), the validation cohort of approximately 200 patients would provide an estimation precision (CI width/2) of $<7\%$, with estimated sensitivity of 90% and specificity of 94%, using CENTERS luminal circumference percentage threshold derived from the training cohort, and high-risk EV prevalence of 40%.

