Key inclusion and exclusion criteria	
Key inclusion criteria: Adult patients with clinically evident or biopsy-confirmed cirrhosis, aged 18 years or older.
 
Key exclusion criteria: has dysphagia, known Zenker's diverticulum, known or suspected gastrointestinal stenosis, pregnancy, active gastrointestinal bleeding, cardiac pacemaker or other implanted electromedical device, life-threatening conditions, plan to undergo magnetic resonance imaging examination before excretion of the MCE, current participation in another clinical study, refusal to give informed consent or any condition that precludes compliance with study.

Number of subjects	591 patients will be required.
Trial duration	
First patient in to last patient out (months): January 2021 to January 2023
 
Duration of the entire trial (months): 36 months
 
Recruitment period (months): 24 months
 
Subject participation duration: approximately two days

Participating Centers	14 centers in China
ClinicalTrials.gov identifier	NCT03748563

Table of content

1 BACKGROUND INFORMATION AND RATIONALE	9
2 STUDY OBJECTIVES AND OUTCOME MEASURES	11
2.1 Primary objective	11
2.2 Secondary objectives.....	11
3 SUMMARY OF STUDY DESIGN	12
4 STUDY RISKS AND BENEFITS	14
4.1 Known potential benefits.....	14
4.2 Potential risks.....	14
4.3 Risk/benefit ratio.....	14
5 STUDY POPULATION.....	15
5.1 Inclusion criteria	15
5.2 Exclusion criteria	15
5.3 Subject Identification and Enrollment.....	15
5.4 Withdrawal	16
6 STUDY METHODOLOGY	17
6.1 Baseline evaluation assessment.....	17
6.2 The ds-MCE and EGD examination procedures.....	17
6.3 Patient satisfaction assessment	23
6.4 Study follow-up	23
6.5 Outcome measures.....	24
7 SAFETY CONSIDERATION	27
7.1 Adverse Events (AE).....	27
7.2 Serious Adverse Events (SAE)	27
7.3 Follow-up of Adverse Events	28
7.4 Monitoring of safety risks	28
8 DATA HANDLING AND RECORD KEEPING	28
8.1 Data collection	28
8.2 Data management and quality.....	29
8.3 Confidentiality and Security.....	29
8.4 Record Retention and Archiving.....	30
9 STATISTICAL CONSIDERATIONS	30
9.1 Hypothesis	30
9.2 Sample size.....	31
9.3 Statistical Analysis Set.....	31
9.4 Statistical Analyses.....	32

10 ETHICAL CONSIDERATIONS.....	35
10.1 Statement of compliance	35

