9.2 Sample size

As a single-arm confirmatory diagnostic accuracy study, we primarily aimed to test whether both the sensitivity and the specificity of ds-MCE for detecting EGV would be $>85\%$. With estimated sensitivity of 90%, specificity of 94%, a two-sided alpha of 5%, power of 80%, EGV prevalence of 62%, and a dropout rate of 3%, 591 patients would be needed.

When considering the accuracy of ds-MCE for detecting high-risk EV (key secondary outcome), the validation cohort of approximately 200 patients would provide an estimation precision (CI width/2) of $<7\%$, with estimated sensitivity of 90% and specificity of 94%, using CENTERS luminal circumference percentage threshold derived from the training cohort, and high-risk EV prevalence of 40%.

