7.3 Statistical Analyses

7.3.1 General Analysis Considerations and Convention

Descriptive statistics for continuous variables will include arithmetic mean (standard deviation) or median (interquartile ranges) as appropriate. Frequency and percentage will be calculated for categorical variables. Unless otherwise specified, for continuous variables, comparisons between groups will be assessed using the paired *t* test or Wilcoxon signed-rank test as appropriate. Categorical variables will be compared using the McNemar test as appropriate.

All statistical analyses will be performed using SAS version 9.4 (SAS Institute Inc, Cary, NC) and R version 4.2.2 (R Foundation for Statistical Computing). Unless otherwise specified, all significance testing will be 2-tailed using $\alpha = 0.05$. Tests will be declared statistically significant if the calculated p-value was <0.05 .

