7.3.4 Multiple Comparisons

Since the primary outcome hypothesis testing based on the two primary endpoints should be met simultaneously, no multiplicity adjustment will be performed.

For the analysis of the secondary and safety outcomes, no adjustment for multiple comparisons will be made.

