7.3.7 Efficacy Analysis

7.3.7.1 Analyses for Primary Outcome

The primary outcome is the diagnostic accuracy of ds-MCE for discrimination of patients with EGV using sensitivity and specificity, along with the corresponding 95% CIs estimated using the Wilson's method¹⁶. Sensitivity and specificity will be compared with 85% using one-sample exact test. The accuracy, and positive and negative predictive values (PPV and NPV) will be calculated as other measures simultaneously, along with the corresponding 95% CIs estimated using the Wilson's method.

- True Positive (a): Both ds-MCE diagnosis and EGD results determine the presence of esophageal or gastric varices, and the location (esophagus or stomach) is consistent.
- False Negative (c): ds-MCE diagnosis determines no cases of esophageal or gastric varices, while EGD results determine the presence of esophageal or gastric varices.
- True Negative (d): Both ds-MCE diagnosis and EGD results determine the absence of esophageal or gastric varices.
- False Positive (b₁): ds-MCE diagnosis and EGD results both determine the presence of esophageal or gastric varices, but the locations (esophagus or stomach) are inconsistent.
- False Positive (b₂): ds-MCE diagnosis determines the presence of esophageal or

gastric varices, while EGD results determine the absence of esophageal or gastric varices.

Table1. Four-grid table for ds-MCE and EGD assessment results

ds-MCE	EGD		Non-varices
	Varices	Inconsistent location in the stomach or esophagus	
Varices	a	b ₁	b ₂
Non-varices	c		d

$$\text{Sensitivity (SE)} = a/(a+b_1+c) \times 100\%$$

$$\text{Specificity (SP)} = d/(b_2+d) \times 100\%$$

$$\text{Accuracy} = (a+d)/(a+b_1+b_2+c+d) \times 100\%$$

$$\text{PPV} = a/(a+b_1+b_2) \times 100\%;$$

$$\text{NPV} = d/(c+d) \times 100\%;$$

Sensitivity Analyses for the Primary Outcome

No sensitivity analysis will be conducted for this study.

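### The stated 80% power with 591 patients is about 2 points optimistic: averaged over the number with EGV, which the design does not fix, the planned exact tests have about 78% power

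*SAP*

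**What the plan says.** SAP 5.3 gives the planning inputs: "With estimated sensitivity of 90%, specificity of 94%, a two-sided alpha of 5%, power of 80%, EGV prevalence of 62" per cent. Protocol 9.2 has the same inputs and ends with "a dropout rate of 3%, 591 patients would be needed"; the protocol synopsis repeats that "591 patients will be required". Neither document gives the formula, the number of patients with EGV behind 591, or whether the 80% applies to each endpoint or to both together. For the method, the SAP cites only a textbook.

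Three other places determine what the power should describe:

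- **The test.** SAP 7.3.7.1: "Sensitivity and specificity will be compared with 85% using one-sample exact test". Under SAP 7.3.1, "all significance testing will be 2-tailed using" a 5% level.
- **The success rule.** SAP 7.3.4 makes no multiplicity adjustment because "the two primary endpoints should be met simultaneously".
- **Who is enrolled.** The disease criterion in SAP 5.2.1 is "Clinically evident or biopsy-proven liver cirrhosis". Presence of varices is not an entry condition, and neither document sets a quota for patients with EGV.

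**The concern.** Only patients with EGV on EGD contribute to sensitivity, and sensitivity is the endpoint that drives the sample size. The plan fixes total enrolment, so the number with EGV will vary around its expected value. For an exact binomial test this matters slightly more than usual. The critical count is an integer, so power moves in a sawtooth as the number of patients changes: it falls a little with each added patient, then jumps by 4 points or so. A sample size set at the first count that reaches 80% sits at the top of a tooth, and most nearby counts lie lower.

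What is at stake is whether the stated 80% describes the study under its own assumptions. The study is described as confirmatory and needs both tests to succeed, so the stated power should match the planned test and that success rule.

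**Working it through.** **Inputs.** From SAP 5.3 and protocol 9.2: null value 85%, sensitivity 90%, specificity 94%, two-sided alpha 5%, EGV prevalence 62%, dropout 3%, 591 enrolled. From SAP 7.3.7.1: one-sample exact test. Two assumptions are added. First, the exact test at two-sided 5% rejects when the exact upper tail at 0.85 is at most 0.025. Second, dropouts are excluded from the analysis.

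**Formula for a fixed count.** For n patients, the critical count c(n) is the smallest c with P(X ≥ c | n, 0.85) ≤ 0.025. Power is P(X ≥ c(n) | n, p), with p = 0.90 for sensitivity and 0.94 for specificity.

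**Reproducing 591.** The smallest n with sensitivity power of at least 80% is 356: c = 316, tail 0.0246, power 80.8%. Then 356/0.62 = 574.2, and 574.2 × 1.03 = 591.4 (574.2/0.97 = 592.0). The normal approximation with null and alternative variances gives 363 patients with EGV and about 604 enrolled, so the exact test fits 591 better. This origin is inferred, because the documents do not show the calculation. The results below do not depend on it.

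At 356 with and 217 without EGV (573 in all), specificity power is 99.4% and joint power is 0.8084 × 0.9939 = 80.3%.

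**The plan's expected split.** 591 × 0.97 = 573.3 evaluable; 573.3 × 0.62 = 355.4 with EGV; 573.3 × 0.38 = 217.8 without. At 355 and 218, joint power is 0.7641 × 0.9936 = 75.9%.

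**Sensitivity power around that count:**

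| With EGV | Critical count | Power at 90% |
|---|---|---|
| 355 | 316 | 76.4% |
| 356 | 316 | 80.8% |
| 358 | 318 | 79.8% |
| 363 | 323 | 77.2% |
| 364 | 323 | 81.5% |
| 370 | 329 | 78.5% |
| 371 | 329 | 82.6% |
| 378 | 336 | 79.2% |
| 379 | 336 | 83.2% |

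Sensitivity power is at least 80% at 356–357, 364–367 and 371–376, and at every count only from 379.

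**Averaging over the number with EGV.** Let M ~ Binomial(573, 0.62). Its mean is 355, its SD is √(573 × 0.62 × 0.38) = 11.6, and its central 95% range is 332 to 378. Over that range sensitivity power runs from 73.2% to 82.6%. Averaged joint power is Σ P(M = m) × power_Se(m) × power_Sp(573 − m).

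| Evaluable | Sensitivity | Specificity | Joint |
|---|---|---|---|
| 573 | 78.4% | 99.1% | 77.8% |
| 574 | 78.5% | 99.2% | 77.9% |
| 591 (no loss) | 79.9% | 99.3% | 79.3% |

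With 573 evaluable, about 75% of the probability falls on counts where sensitivity power is below 80%.

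**Robustness.** Treating dropout as random, Binomial(591, 0.97), leaves joint power at 77.8%. The other common two-sided exact rule (minimum likelihood) gives 78.6% for sensitivity and 77.9% jointly at 573.

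**Scale.** Averaged sensitivity power at 573 is 57% if true sensitivity is 89% and 93% if it is 91%. It is 77.0% if prevalence is 60% and 80.6% if it is 65%.

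**The case against.** The strongest reply is that planning at an expected case count is ordinary practice. Read that way, the calculation reproduces, and neither document claims that its 80% is averaged over a random number with EGV. That stands as a defence of 591. It does not fully defend the 80%: the plan's inputs give 355.4 patients with EGV, and the planned exact tests reach 80% at 356 but neither at 355 nor on average. The documents do not say that the 80% is conditional on a particular count.

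A second reply is that the gap is smaller than the rounding in the inputs. This is true. At 573 evaluable, averaged sensitivity power rises from 78.4% to 80.3% if true sensitivity is 90.1%, and joint power reaches 81.3% at 90.2%. That limits the importance of the point, but the stated power should still follow from the stated inputs.

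Third, the 78% assumes that dropouts leave the analysis. SAP 7.3.3 applies worst-outcome imputation to missing primary-endpoint data in the mITT analysis, while SAP 7.2 restricts the mITT set to patients evaluable for EV and GV. How the two combine is not settled, so the assumption has to be stated with the figure.

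Finally, on the protocol's planned timetable recruitment ended before the final SAP of May 2023, and power does not alter a reported confidence interval. That is a reason to confine the remedy to wording.

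A reader might infer that 591 was miscalculated, or that the study is materially underpowered and needed more patients. The documents support neither. 591 is consistent with the planned test at 356 patients with EGV, and the average shortfall is about 2 points.

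**Conclusion.** The point holds as a minor correction to a planning statement. Under the plan's own assumptions, power averaged over the number with EGV is 78.4% for sensitivity, 99.1% for specificity and 77.8% for both. That is 1.6 points below 80% if the 80% was meant for sensitivity alone, and 2.2 points below if it was meant jointly; the documents do not say which. With no dropout the joint figure is 79.3%, under 1 point short.

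The result rests on the exact upper-tail 0.025 rule, on dropouts being excluded, and on the stated 90%, 94%, 62% and 3%. It does not rest on the inferred origin of 591. It affects no estimate, confidence interval or hypothesis test, and it matters less than the uncertainty in the assumed sensitivity.

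**What to change.** Replace the power sentence in SAP 5.3 and protocol 9.2 with:

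*With 591 enrolled and about 573 evaluable after 3% dropout (dropouts excluded), the expected number with EGV is about 355. Because this number is not fixed, the exact tests have on average about 78% power to show both sensitivity and specificity >85% (about 78% and 99% separately). Joint power of 80% is attained at 356 patients with EGV but not at every nearby count.*

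The wording should keep the words on average, because the single split of 355 with and 218 without EGV gives 75.9%, and a reader checking that split alone would not obtain 78%.

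The cost is one passage of text in each document. Enrolment, data and analysis do not change. The only downside is a stated power about 2 points less favourable.
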